2.2.1.3. Exploratory Efficacy Endpoint

The exploratory efficacy endpoint is a characterization of Th17 response by enzyme linked immune assay.

2.2.2. Safety Endpoints

Safety of intradermally administered TNX-2100 SARS-CoV-2 peptides, as measured by:

- Incidence of AEs.
 - Clinically abnormal symptoms and other AEs will be assessed as defined in the FDA Guidance for Industry: “Toxicity Grading Scale for Healthy Adult and Adolescent Volunteers Enrolled in Preventive Vaccine Clinical Trials” using a 4-point system (Grade 1 = mild, Grade 2 = moderate, Grade 3 = severe, and Grade 4 = potentially life threatening).
 - Adverse events of systemic allergic reaction will be graded according to the World Allergy Organization Grading Scale for Systemic Allergic Reactions.
 - Local skin reactions will be captured by a subject self-reported 7-point Likert scales indicating severity of: erythema, pain, pruritis, and swelling.

- Protocol-defined adverse events of special interest (AESI):
 - Anaphylactic reaction.
 - Enhanced disease from repeated exposure to SAR-CoV-2 (in subjects who have recovered from SARS-CoV-2 infection or in subjects recently vaccinated against SARS-CoV-2).

2.3. Modified Evaluation

Because the outcome of area of induration for the DTH reactions was not as anticipated, the DTH reactions will not be statistically analyzed. Any primary, secondary, or exploratory efficacy endpoint will be omitted from the analysis and only safety will be assessed.

3. Overall Study Design and Plan

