### **13.6. Efficacy Analyses**

The efficacy analyses include primary, secondary, and exploratory endpoints as outlined in [Section 7.2.2](#). Efficacy analyses will be conducted using the mITT population.

The frequency and percentage of subjects with a maximal area of induration of  $\geq 5$  mm will be summarized within each cohort and by overall subjects.

Cytokine and cell surface T-cell phenotype markers will be summarized descriptively within each cohort and by overall subjects.

Enzyme linked immune assay parameters will be summarized descriptively by study visit within each cohort and by overall subjects.

Results obtained from subjects deemed to be T-cell-specific immunodeficient will be collected, documented and reported, but will not be included in the analysis of the efficacy of the assay to detect a DTH response to SARS-CoV-2 peptides.

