2.1. Study Objectives

2.1.1. Primary Objective

The main objectives of the study are to evaluate the safety of intradermally-injected synthesized TNX-2100 SARS-Co V-2 peptide antigens and to assess the presence of DTH reactions in response to intradermal injection of synthesized TNX-2100 SARS-Co V-2 peptide antigens.

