2.2. Study Endpoints

2.2.1. Efficacy Endpoints

2.2.1.1. Primary Efficacy Endpoint

The primary efficacy endpoint of this study is the maximal area of induration ≥ 5 mm at injection sites on the volar aspect of the forearms at 48 hours, 72 hours, and 96 hours post skin test administration.

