9.6. Concomitant Medication

Prior and concomitant medications will be listed. Medications that started before initial intradermal injections of investigational products will be considered prior medications whether or not they were stopped before initial intradermal injections of investigational products. Any

medications continuing or starting after initial intradermal injections of investigational products will be considered to be concomitant. If a medication starts before initial intradermal injections of investigational products and continues after, it will be considered both prior and concomitant.

Medications will be coded using World Organization Drug Dictionary Anatomical Therapeutic Chemical classes and preferred terms.

10. Changes from Planned Analysis

Because the outcome of area of induration for the DTH reactions was not as anticipated, the DTH reactions will not be statistically analyzed. Any primary, secondary, or exploratory efficacy endpoint will be omitted from the analysis and only safety will be assessed.

11. Other Planned Analysis

Not applicable for this study.

12. References

ASA. (2018) Ethical Guidelines for Statistical Practice. Prepared by the Committee on Professional Ethics, April 2018. <http://www.amstat.org/about/ethicalguidelines.cfm>

ICH (1998). ICH Harmonised Tripartite Guideline. Statistical Principles for Clinical Trials E9; 1998. https://database.ich.org/sites/default/files/E9_Guideline.pdf

RSS. (2014) The Royal Statistical Society: Code of Conduct, 2014. <https://rss.org.uk/about/policy-and-guidelines/code-of-conduct/>.

ELECTRONIC RECORD AND SIGNATURE DISCLOSURE

From time to time, [REDACTED] (we, us or Company) may be required by law to provide to you certain written notices or disclosures. Described below are the terms and conditions for providing to you such notices and disclosures electronically through the DocuSign system. Please read the information below carefully and thoroughly, and if you can access this information electronically to your satisfaction and agree to this Electronic Record and Signature Disclosure (ERSD), please confirm your agreement by selecting the check-box next to 'I agree to use electronic records and signatures' before clicking 'CONTINUE' within the DocuSign system.

Electronic Signature Responsibilities

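### SAP 2.3 and Section 10 drop the primary and every other efficacy endpoint for an undefined, outcome-dependent reason, leaving a main objective with a by-subject listing in place of the summary planned in protocol 13.6

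*SAP*

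**What the plan says.** The SAP keeps the objective and the endpoint. Section 2.1.1 names, as one of two main objectives, "to assess the presence of DTH reactions in response to intradermal injection of synthesized" TNX-2100 peptide antigens. Section 2.2.1.1 begins: "The primary efficacy endpoint of this study is the maximal area of induration", with a threshold of 5 mm and readings at 48, 72 and 96 hours.

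Section 2.3 then withdraws the analysis: "Because the outcome of area of induration for the DTH reactions was not as anticipated, the DTH reactions will not be statistically analyzed". Section 10, Changes from Planned Analysis, repeats this and states its scope: "Any primary, secondary, or exploratory efficacy endpoint will be omitted from the analysis and only safety will be assessed". What remains for DTH is the listing by subject and visit in SAP 8.5.

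Protocol 13.6 plans a descriptive efficacy analysis in the mITT population:

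- "The frequency and percentage of subjects with a maximal area of induration of" at least 5 mm, within each cohort and overall.
- "Cytokine and cell surface T-cell phenotype markers will be summarized descriptively within each cohort and by overall subjects".
- A matching descriptive summary of the enzyme-linked assay results used for Th17.
- An exclusion: "Results obtained from subjects deemed to be T-cell-specific immunodeficient will be collected, documented and reported, but will not be included in the analysis" of how well the test detects a DTH response.

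**The concern.** The SAP removes the planned summary of a main objective because of how that objective's data turned out. It does not say what was unexpected. Few reactions at the TNX-2100 sites, a reactive diluent or a non-reactive CANDIN would each fit the wording, and each would mean something different for the product. None of them makes a count and a percentage impossible.

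What is at stake is the reporting of the trial's purpose. Protocol 5.3 says that the best-performing peptide mixture and dilution will go forward to a larger confirmatory study. Under this SAP that choice would have no tabulated response rate behind it, for any cohort, product or strength.

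**Working it through.** The documents give no power, alpha or effect size, so there is no stated figure to reproduce. The check is mainly a comparison of text.

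**1. Does the SAP withdraw the objective or endpoint?** No. Sections 2.1.1 and 2.2.1 still state them. Section 6 still defines the mITT population but assigns it no output: safety tables use the Safety Population and listings use Enrolled Subjects.

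**2. What is omitted?** Counting SAP 2.2.1: 1 primary + 4 secondary (three DTH correlations and Th1/Th2) + 1 exploratory (Th17) = 6 endpoints.

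**3. Does the reason cover all six?** The primary endpoint and the three correlations use induration. Th1/Th2 and Th17 do not: 6 − 4 = 2. They come from blood which, under protocol 12.1.8, is drawn at Visit 1 before the product is given, and protocol 13.6 gives them their own summaries. An unexpected skin result cannot explain dropping them.

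**4. How much DTH data is left as a listing?** Three products × 2 strengths = 6 TNX-2100 sites; with diluent and CANDIN, 8 sites. At three reading times that is 6 × 3 = 18 product readings and 8 × 3 = 24 readings in all per subject, or 24 × 90 = 2,160 at the planned 90 subjects.

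**5. Would a poor result be uninformative if tabulated?** No. The counts here are assumed, because the documents give no results; all planned subjects are taken as evaluable. The intervals are exact (Clopper-Pearson) 95%. For zero responders the upper limit is 1 − 0.025^(1/n).

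| Assumed result | Rate | 95% interval |
|---|---|---|
| 0/30 (one cohort) | 0% | 0 to 11.6% |
| 3/30 | 10% | 2.1 to 26.5% |
| 15/30 | 50% | 31.3 to 68.7% |
| 0/90 (overall) | 0% | 0 to 4.0% |

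Even no responders in a cohort would bound the response rate below about 12%.

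**6. Does another provision replace the summary?**

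- SAP 1 allows post-hoc analyses but does not require any.
- Protocol 13.7 plans an analysis of DTH presence once all subjects have passed Visit 5. The SAP text does not mention it, and nothing shows whether DTH was tabulated there.
- The protocol synopsis and the opening of protocol 13 leave details and variable definitions to the SAP. That does not plainly extend to removing the primary endpoint.

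**The case against.** The best defence is that this was a small, open-label proof-of-concept study with no formal sample size calculation and only descriptive efficacy analyses. No error rate or power is affected, and under this SAP no efficacy analysis is left to support a claim. The change is disclosed under its own heading, and DTH responses are still listed. All of that stands. It shows that the departure was open; it does not supply the missing rates or the missing explanation.

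Three stronger readings are tempting, and the documents do not support them.

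- *A reader cannot tell a null result from a failed control.* SAP 8.5 lists DTH responses by subject and visit, SAP 9.1 lists all collected data, and neither excludes the control sites. Someone with the listings could count them. The supportable statement is that neither TNX-2100 nor control rates are tabulated, and neither outcome is explained.
- *The mITT wording drops non-reactors and so inflates the rate.* The definition is not limited to TNX-2100 sites, and protocol 12.1.10 expects CANDIN to be positive, so most subjects would qualify even if a reaction were required. Protocol 11 also speaks of the size of the response at the negative control, which favours the meaning of a measured reading.
- *SAP 2.3 removed the planned analyses of sensitivity and specificity, best antigen and concentration, best timepoint, and correlation with T-cell response.* Protocol 13.6 sets out no method for any of these, so that gap came before SAP 2.3.

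**Conclusion.** The point holds and should be fixed before the SAP is used. All six efficacy endpoints are omitted for a reason that depends on the observed result and is not defined. For two of the six the reason cannot apply. One of two main objectives is left with a listing and no cohort rate, contrary to protocol 13.6.

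Confidence is high for the conflict in the text and lower for its consequences. The documents do not show how induration departed from expectation, whether the controls behaved as expected, whether the blood assays were run, or whether the Visit 5 analysis tabulated DTH. A reader might infer concealment or a negative result; the disclosure in Section 10 speaks against the first, and nothing in the documents establishes the second. The intervals above are illustrations at the planned cohort sizes.

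**What to change.** Delete the omission in SAP 2.3 and Section 10, and make four changes.

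1. **Restore the protocol 13.6 table.** Give n (%) with a DTH response of at least 5 mm (mean of the two diameters, protocol 12.1.10), by cohort and overall, in mITT. Show it for each product and strength, with diluent and CANDIN in separate rows. State that any recorded reading, including 0 mm, counts as an induration response for mITT. Apply the exclusion of subjects deemed T-cell-specific immunodeficient, and show the table with and without it: neither document defines the rule, and induration results are already known.
2. **Restore the blood summaries.** Give descriptive Th1/Th2 and Th17 results (protocol 13.6) and antibody results (protocol synopsis), or state that the assays were not run.
3. **Explain the change in Section 10.** Say what was unexpected, whether diluent and CANDIN behaved as protocol 12.1.10 expects, and whether the decision followed the Visit 5 analysis. If the controls failed, keep the table and qualify its interpretation.
4. **Label as post hoc, as SAP 1 requires, whatever 13.6 does not specify.** This covers an any-site row, a maximum over 48, 72 and 96 hours, exact intervals, results by reading time, sensitivity and specificity against clinical history, and the T-Detect and antibody correlations.

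The cost is SAP wording and a few descriptive tables from readings that the SAP already lists. The blood summaries cost little more if the assays were run. The display by product and strength, the control rows, the mITT clarification and the with/without display clarify 13.6 rather than restore it, and the SAP should say so.

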3.1. Overall Design

This will be a proof-of-concept (POC), dose finding, multi-cohort study designed to evaluate the safety of intradermally-injected synthesized TNX-2100 SARS-CoV-2 peptide antigens and assess the presence of DTH reactions in response to intradermal injection of synthesized TNX-2100 SARS-CoV-2 peptide antigens. This study will be conducted in a total of approximately 90 subjects (30 subjects per cohort) who are either uninfected/unexposed healthy individuals (Cohort 1), who are confirmed to have recovered from SARS-CoV-2 infection, independent of vaccination status (Cohort 2) or who have received a complete SARS-CoV-2 vaccine course with no known history of natural infection (Cohort 3).

The study will consist of a baseline/skin test administration at Visit 1 (Day 1) at which time baseline assessments are to be completed, the skin test is performed, and appropriate test samples are collected. Follow-up visits to monitor safety and evaluate the presence or absence of DTH reactions will be conducted per the following schedule: Visit 2 (Day 2); Visit 3 (Day 3); Visit 4 (Day 4); Visit 5 (Day 5). Safety monitoring will continue at Visit 6 (Day 30) and Visit 7 (Day 180) by telephone calls. The estimated study duration will be approximately 6 months. Photography of the injection site (volar forearms) after IP administration at Visit 1 and at Visit 3, 4, and 5, or unscheduled in person visits, will be used for safety documentation of local skin reaction, such as redness and swelling, or unexpected findings such as rash, blistering and necrosis, which require assessment by the designated Investigator.

Eligible subjects who provide written informed consent and who satisfy eligibility criteria will undergo a nasopharyngeal swab for a polymerase chain reaction (PCR) (reverse transcriptase [RT]-PCR or other) test to detect active SARS-CoV-2 infection. A laboratory PCR test or a sponsor approved rapid PCR test (such as the AcculaTM RT-PCR test) may be used. If a laboratory PCR test is used, subjects will complete a Screening Visit between Day -2 and Day -1 to allow processing of the sample prior to the Baseline/Skin Test Administration Visit 1 (Day 1). The rapid PCR test can be performed at Visit 1 (Day 1) and is preferred to facilitate enrollment by reducing the number of required site visits. If the test result is negative, the subject will

proceed with the required blood draws followed by intradermal injection of the investigational products (IPs) and controls.

3.2. Sample Size and Power

Formal sample size calculations were not performed. The number of subjects were chosen based on feasibility and are considered sufficient to meet the study objectives. Approximately 90 subjects (30 subjects per cohort) will be enrolled.

3.3. Study Population

The study population consists of male and female adults, aged 18 to 65 years of age, inclusive. Subjects will be uninfected/unexposed healthy individuals (cohort 1), SARS-CoV-2 convalescent subjects (cohort 2), or SARS-CoV-2 vaccinated subjects (cohort 3).

3.4. Treatments Administered

Intradermal injections will be administered in two stages. At Stage 1, each subject will receive the diluent (negative control), followed by the “1:10 dilution” strength of TNX-2110, TNX 2120 and TNX 2130 in their left forearm, and a CANDIN® (positive control) in their right forearm. If no systemic adverse reactions or unusual local site reactions per the Principal Investigator’s (PI) judgement are observed during 60 minutes after Stage 1 administration, the subjects will proceed to Stage 2.

At Stage 2, Subjects will receive the “undiluted” dose strength of TNX-2110, TNX-2120, TNX-2130 in the right forearm in the order and at the specific location. If no evidence of systemic adverse reactions or unusual local site reactions, per the PI’s judgement, have occurred during the 30 minutes post-administration, subjects will be free to leave the clinic. Subjects will be instructed to keep the injection sites clean, uncovered, and to not scratch or rub the area.

In total, each subject will receive 8 intradermal injections (four per forearm), spaced two inches apart at pre-determined sites on the volar aspect of the forearms.

3.5. Method of Assigning Subjects to Treatment Groups

Subjects will be enrolled in parallel into 3 cohorts according to the inclusion/exclusion criteria:

- Cohort 1: 30 healthy uninfected/unexposed subjects.
- Cohort 2: 30 subjects who have recovered from SARS-CoV-2 infection at least two months prior to enrollment into the study independent of vaccination status.
- Cohort 3: 30 subjects who have received a complete SARS-CoV-2 vaccine course at least four weeks prior to enrollment into the study no known history of natural infection.

3.6. Blinding and Unblinding

This will be an open-label study.

3.7. Schedule of Events

The full schedule of activities can be found in Table 3 of the protocol.

4. Statistical Analysis and Reporting

4.1. Introduction

Data processing and tabulation of descriptive statistics will use SAS (release 9.4 or higher), unless otherwise noted. If the use of other software is warranted, the final statistical methodology report will detail what software was used for what purposes.

Continuous (quantitative) variable summaries will include the number of subjects (n) with non-missing values, mean, standard deviation (SD), median, minimum, and maximum.

Categorical (qualitative) variable summaries will include the frequency and percentage of subjects who are in the particular category or each possible value. In general, the denominator for the percentage calculation will be based upon the total number of subjects in the study population for the cohorts, or other describing characteristic, unless otherwise specified. The denominator for by-visit displays will be the number of subjects in the relevant study population with non-missing data at each visit.

The minimum and maximum will be reported with the same degree of precision (i.e., the same number of decimal places) as the observed data. Measures of location (mean and median) will be reported to 1 degree of precision more than the observed data and measures of spread (SD) will be reported to 2 degrees of precision more than the observed data.

Percentages will be presented to 1 decimal place, unless otherwise specified.

5. Study Halting and Stopping Rules

Dosing may be halted temporarily to investigate before the entire study is terminated. If any of the below events occur, enrollment and dosing should be paused study-wide pending review by the Sponsor, Investigator, and/or Medical Monitor. Subjects enrolled in the study must continue to be followed for the duration of the study.

- One or more subjects with a serious adverse event (SAE) considered definitely, probably, or possibly related to the IPs.
- Three or more subjects with the same or similar grade 3 or higher AEs of the same type considered definitely, probably, or possibly related to IPs.
- One AESI, considered at least possibly related to the IPs.

6. Analysis Populations

The following analysis populations are planned for this study:

- **Safety Population:** includes any subjects in Cohort 1, 2, or 3 who receive at least 1 intradermal injection of the IPs. This population will be used for all safety tables.

- **Intent-to-Treat (ITT) Population:** includes any subjects in Cohort 1, 2, or 3 who provide written informed consent, satisfy all inclusion/exclusion criteria, and have a negative test result from RT-PCR detection of SARS-CoV-2 viral RNA.
- **Modified Intent-to-Treat (mITT) Population:** includes subjects from ITT who complete stages 1 and 2 of administration and have induration responses for at least one post skin test administration visit at hour 48, 72, or 96.
- **Enrolled Subjects:** includes subjects who have been consented and screened, with eligibility verified. This population will be used for all listings.

7. General Issues for Statistical Analysis

7.1. Statistical Definitions and Algorithms

7.1.1. Baseline

The last observation recorded before the first intradermal injection of the IPs will be used as the baseline observation for all calculations of change from baseline.

7.1.2. Adjustments for Covariates

Not applicable to this study.

7.1.3. Multiple Comparisons

There will be no adjustments for multiple comparisons.

7.1.4. Handling of Dropouts or Missing Data

Any subject who withdraws from the study will not be replaced.

Unless specified otherwise in any of the previous sections, missing data will not be imputed.

7.1.5. Analysis Visit Windows

Data will be summarized by nominal study visit recorded in the database.

For tabulated summaries, only the scheduled visits will be included. Unscheduled assessments will be listed.

7.1.6. Derived Variables

- Change from baseline = value at current time point – value at baseline.

- TEAE = any adverse event with an onset date/time after the first intradermal injection of the IPs.

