### **12.2.1. Screening Visit (Day -2 to -1)**

The Screening Visit is only required if a laboratory PCR test will be used to detect presence of active SARS-CoV-2 infection. The following procedures will be performed by the study personnel in the order given:

- Informed Consent: Before the potential subject has undergone any study-related screening procedures, the nature of the TNX-CA-C201 study, and the potential risks associated with it, will be explained to the subject, and the subject will be given an opportunity to ask questions to his or her satisfaction. After the questions are answered, but before proceeding further, the subject must read and sign a written ICF for protocol TNX-CA-C201. The signed ICFs will be retained in the Investigator's study file, and the date the subject signed the forms will be entered into the CRF. The subject will be provided with a copy of his or her signed and dated ICFs. The subject will be required to sign all updated informed consents.
- Perform nasopharyngeal swabbing for SARS-CoV-2 viral RNA detection via laboratory PCR test (note this result must be negative before proceeding to blood sample collection and skin test administration).

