## **14. DEFINITIONS, RECORDING, AND REPORTING OF ADVERSE EVENTS**

### **14.1 Definition of Adverse Events**

Any untoward medical occurrence in a patient or clinical investigation subject administered a pharmaceutical product and which does not necessarily have a causal relationship with this treatment. An AE can therefore be any unfavorable and unintended sign (including an abnormal laboratory finding), symptom, or disease temporally associated with the use of a medicinal (investigational) product, whether or not related to the medicinal (investigational) product.

A treatment-emergent adverse event (TEAE) is an AE that either commenced following initiation of study treatment or was present prior to study treatment but increased in frequency or severity following initiation of study treatment.

Other untoward events occurring in the framework of a clinical study will be recorded as AEs, e.g., those occurring during treatment-free periods (including Screening or post-treatment follow-up periods; see the Schedule of Activities, [Table 3](#)) in association with study-related procedures and assessments, or under placebo. For study drugs, lack of efficacy may be an expected potential outcome and should not be reported as an AE unless the event is unusual in some way, e.g., greater in severity.

Concomitant illnesses, which existed prior to entry into the clinical study, will not be considered AEs unless they worsen during the treatment period. Pre-existing conditions will be recorded as part of the subject's medical history.

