#### **14.2.2 Severity of Adverse Event**

The severity of an AE refers to the extent of clinical abnormalities and to the extent of which an AE affects the subject's daily activities ([Table 8](#), FDA Guidance for Industry; Toxicity Grading Scale for Healthy Adult and Adolescent Volunteers Enrolled in Preventive Vaccine Clinical Trials, 2007). The term "severity" is used to describe the intensity of an event. This is not the same as "serious". Seriousness, not severity, serves as the guide for defining regulatory reporting

obligations. The highest severity grade attained should be reported, for AEs with divergent severities.

Severity will be categorized according to event category (local, systemic, other).

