9.1. Adverse Events

Treatment emergent AEs are defined as AEs that either commenced following initiation of study treatment or was present prior to study treatment but increased in frequency or severity following initiation of study treatment. Adverse events of special interest (AESI) include anaphylactic reaction and enhanced disease from repeated exposure to SARS-CoV-2 (in subjects who have recovered from SARS-CoV-2 infection or in subjects recently vaccinated against SARS-CoV-2).

All AEs occurring after completion of the informed consent process and before the end of study, regardless of relationship to study drug, will be included and classified by system organ class (SOC) and preferred term (PT) using the Medical Dictionary for Regulatory Activities (MedDRA) v24.0.

For treatment-emergent AEs (TEAEs), the following will be summarized and presented for the Safety population:

An overall summary of TEAEs, which includes:

- a. the number and percentage of patients experiencing a TEAE
- b. the number and percentage of patients experiencing a TEAE by strongest relationship to IP
- c. the number and percentage of patients experiencing a TEAE by highest severity grade
- d. the number and percentage of patients experiencing a systemic allergic reaction by highest grade according to the World Allergy Organization Grading Scale for Systemic Allergy Reactions
- e. the number and percentage of patients experiencing a treatment emergent SAE (TESAE)
- f. the number and percentage of patients experiencing a TEAE leading to study discontinuation
- g. the number and percentage of patients experiencing a treatment emergent AE of Special Interest

In the overall summary of TEAEs table, besides tabulating the number and percentage of patients, the total number of TEAE episodes will also be provided. If a patient has repeated episodes of a particular TEAE, all episodes will be counted in the summary table.

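### SAP 7.1.6 leaves out the worsening part of the TEAE definition given in SAP 9.1 and protocol 14.1, and cannot classify injection-day adverse events that have no onset time

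*SAP*

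**What the plan says.** Section 7.1 of the SAP holds its statistical definitions and algorithms. Under Derived Variables (7.1.6) it gives the rule "TEAE = any adverse event with an onset date/time after the first intradermal injection of the IPs".

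SAP 9.1, which introduces the TEAE summary, starts from events that begin once treatment has started and adds a second part: "or was present prior to study treatment but increased in frequency or severity following initiation of study treatment". Protocol 14.1 has the same two-part definition.

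Four other provisions bear on the flag:

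- **Collection period (SAP 9.1).** "All AEs occurring after completion of the informed consent process and before the end of study" are included, so events between consent and injection are in the data.
- **Recording of change (protocol 14.2.2).** "The highest severity grade attained should be reported, for AEs with divergent severities". Neither document says whether a worsened event gets a new record or a worsening date.
- **Dates and times (SAP 7.1.7).** If only the day is missing and the month and year match the first dose, the start date becomes the first-dose date. If the month is missing too, the same happens under stated conditions. In both cases a date that would fall after the end date is moved earlier. Missing times stay missing.
- **Counting (SAP 9.1).** The overall summary reports subjects and episodes: "If a patient has repeated episodes of a particular TEAE, all episodes will be counted in the summary table".

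**The concern.** The section that a programmer would code from omits a category that the protocol and the SAP's own safety section include. Protocol section 13 promises exact variable definitions in the SAP; on this variable the SAP gives two. SAP section 10 lists only the dropped efficacy analysis as a change.

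The second gap is of a different kind. The date imputation itself creates injection-day onsets with no time, and a rule built on the word *after* cannot place them.

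SAP 2.3 drops all efficacy analysis and SAP 8.5 only lists the DTH responses. The overall TEAE summary is the only tabulation that SAP section 9 specifies; laboratory tests, vital signs, physical examination and ECG are listed. Two programmers who both follow the SAP could therefore report different subject and episode counts from the same data.

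**Working it through.** The plan states no figure to reproduce, so the check applies each rule to constructed cases and then scales the effect of one reclassification.

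**Step 1. Apply both rules.** Assume injection on Day 1 at 10:00 (an illustration; the documents fix no clock time).

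| Adverse event | SAP 7.1.6 | SAP 9.1 / protocol 14.1 |
|---|---|---|
| Onset Day -1, no worsening | not TEAE | not TEAE |
| Onset Day -1, worsens after injection | **not TEAE** | **TEAE** |
| Onset Day 1 08:00, worsens after injection | **not TEAE** | **TEAE** |
| Onset Day 1 11:00 | TEAE | TEAE |
| Onset Day 1, time missing | undetermined | undetermined |
| Day missing, imputed to Day 1, time missing | undetermined | undetermined |
| Onset Day 2, time missing | TEAE | TEAE |

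Rows 2 and 3 are the contradiction. Rows 5 and 6 are the missing-time gap. It is the same under either definition, so aligning the definitions does not close it.

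**Step 2. Resolve rows 5 and 6 by date alone.** Under *date later than injection date*, every such event is excluded, including a reaction that truly began at 11:00 but was not timed. Under *date on or later than injection date*, every such event is included, including one that began at 08:00. The SAP chooses neither.

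**Step 3. How wide is the window for rows 2 and 3?** Protocol 12.2.1 says "The Screening Visit is only required if a laboratory PCR test will be used to detect presence of active SARS-CoV-2 infection". With the preferred rapid test, consent and injection fall on the same day. With a laboratory test, consent is on Day -2 or Day -1, which is 1 to 2 days before Day 1 if there is no Day 0. The event must start in that window, worsen after injection and stay as one record with its original onset. It can happen: the blood draw, and the swab if the rapid test is used, precede injection on Day 1 (protocol 12.2.2).

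**Step 4. Scale.** SAP 4.1 and section 6 make the denominator the Safety Population, that is, the n subjects dosed. If k affected subjects have no other TEAE, incidence moves by k/n.

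- k = 1, n = 30 (planned cohort): 1/30 = 3.3 points.
- k = 1, n = 90 (planned total): 1/90 = 1.1 points.
- k = 1, n = 20 (assumed, if a cohort falls short): 1/20 = 5.0 points.
- A subject who already has a TEAE moves incidence by 0. This may be common, because observed injection-site changes are recorded as AEs (protocol 12.1.11) and each subject has eight injections.
- The episode count changes by 1 per affected event in either case.

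Omitting worsening can only lower the counts. The direction of the missing-time gap depends on the comparison chosen in step 2. The documents do not give k, and none is assumed.

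**The case against.** The strongest reply is that this is a minor wording edit. SAP 9.1 states the protocol's definition immediately before the table it governs, so it is the natural reading, and the silence of SAP section 10 fits the view that no narrowing was meant. The window is short. Illnesses that predate entry are largely outside the problem: "Concomitant illnesses, which existed prior to entry into the clinical study, will not be considered AEs unless they worsen during the treatment period". Such an event may then carry a post-injection onset, although the documents do not say which onset date is entered. On missing times, subjects are watched on site for 60 and then 30 minutes and onset time is a listed field, so immediate reactions are the likeliest to be timed. Imputing to the first-dose date rather than the first of the month suggests an intent to treat such events as treatment-emergent.

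Most of this stands and limits the size. It does not say which section prevails, and the likely intent behind the imputation is defeated by the word *after*.

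Four stronger readings are tempting, and the documents do not support them:

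- **That the two anchors really differ, by the diluent injection.** SAP 3.4 says "At Stage 1, each subject will receive the diluent (negative control), followed by" the diluted peptides, so a reader might infer that study treatment starts before the first IP. But protocol 10.1 names three IPs, while 10.3 counts the diluent vials among those holding investigational product. Whether the anchors differ is open. Anchoring TEAEs to the diluent could also separate them from baseline (SAP 7.1.1), the Safety Population (section 6) and prior or concomitant medication (9.6), all of which use the IP injection.
- **That 3.3 and 1.1 points are upper bounds.** They rest on planned sizes of about 30 and 90, and on one affected subject.
- **That the telephone visits will produce many unclassifiable events.** Visits 6 and 7 ask about events since the last site visit, normally Day 5. A new event first reported there is normally known to follow injection, even though SAP 7.1.7 does not use that knowledge.
- **That the TEAE summary is the only AE tabulation in either document.** Protocol 13.5.1 also plans AE tables by system organ class, preferred term, severity and causality, with no TEAE restriction. The statement holds only for SAP section 9.

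**Conclusion.** The point holds. SAP 7.1.6 conflicts with SAP 9.1 and protocol 14.1 for an event that starts before injection and worsens afterwards. SAP 7.1.6 and 7.1.7 together leave an injection-day event without a time unclassified. Confidence in both findings is high because they follow from the text.

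The effect is probably small. It requires a pre-injection event kept under its original onset, or a missing time or day. Every AE remains in the listings, and the halting rules in SAP section 5 do not use the flag. Per affected subject with no other TEAE the shift is 1/n of those dosed; the number of such subjects cannot be derived from the documents. The correction should be made because a stated rule gives a conflicting or undetermined result for the one table in SAP section 9, and correcting it takes a few sentences.

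**What to change.** 1. **One definition.** Replace the 7.1.6 rule with the two-part definition in SAP 9.1 and protocol 14.1. State that initiation of study treatment means the first intradermal injection of the IPs, the anchor already used for baseline, the Safety Population and prior or concomitant medication.
2. **Identifiable worsening.** Enter a post-injection worsening as a new AE record with its own onset, or record a worsening date. If the data are already collected, query only AEs with onset between consent and injection.
3. **Missing-time rule.** Count an AE dated or imputed to the injection day with no time as a TEAE, unless other recorded data, such as a resolution time, show that it began before injection and did not worsen.

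The cost is a few SAP sentences, one programming rule, and a small recording convention or a limited site query. The downside is that a few pre-injection events may be counted as TEAEs.
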